The two-day training developed by Drs. [name], [name] and [name] will be informed by previous staff training in community clinics using the ACP guide and brief counseling framework. The session will take place in a central location and will include discussion of roles and responsibilities of the health coach for this project, and a review of the counseling framework. Skill-building will focus on brief education and coaching to facilitate patients' setting health goals and creating highly specific and easily achievable action plans. Training will also include skill building in motivational interviewing, clear communication and use of health literacy best practices (slowing down, using plain language, reducing numeracy demands, pointing out key messages in the guide book and using teach-back to confirm understanding). The theory-based training is designed to improve health coaches' capacity to enhance patients' understanding of their disease and problem-solving ability to change their health behavior and adhere to their action plans. The training will also focus on effective telephone counseling and follow up, employing strategies developed in previous research to reach patients by phone. Instruction will also be provided on use of a tracking system to recorded number of contacts (phone and in person), length of time spent in each contact, number of attempts to reach patients, and the content of each session.

Nurse training will cover an overview of the usual care diabetes materials in the enhanced usual care arm only (the "Living Well with Diabetes: a self-care workbook"). A review of the standards for usual care delivery will be provided to avoid contamination, as well as training on the tracking system. This will be provided by the Director of Research for the family medical centers in collaboration with the study team.

Randomization. After the initial phone call to recruit participants, the RA will assign patients interested in participating to either the intervention or to the enhanced usual care arm based on an allocation table created prior to study recruitment using a simple 1:1 randomization scheme, stratified by site. Patients will receive a \$30 Walmart gift card at baseline, a \$30 Walmart gift card at 3 months and a \$30 Walmart gift card at 6 months for their participation. If the patient has a phone call for the 3 month follow-up, they can get their gift card the next time they come into clinic

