eligibility criteria: 1) 21 years of age or older, and 2) English speaking. The exclusion criteria are: 1) uncorrectable vision, hearing, or cognitive impairments that limit the ability to access intervention materials; and 2) those who are too ill to participate due to recent hospitalization or other recently documented illnesses. The English speaking criterion is included because not all measures and materials involved in the clinical trial are available in languages other than English.

We will recruit 750 patients (n=375 per arm). Eligible participants will be identified through EHR queries. The Central RA/care coordinator will make all pre-visit calls to eligible patients. The Central RA/care coordinator will provide information about the study in the pre-visit call, and ask if the patient is interested in participating in the study. If the patient is interested, the Central RA/care coordinator will ask the patient to meet with the Site RA for about 1 hour, review and sign the informed consent document, and begin baseline data collection. At each clinic, the Site RA will receive lists of interested patients and their scheduled appointment times, greet patients upon check in and escort them to a private space, explain the study, answer any questions the patient might have, and obtain written consent. The Site RA will then collect baseline data through a structured interview. Participants who are randomized to the intervention arm will also meet with the health coach for about 30 minutes. Participants will also meet with their provider if scheduled.

Informed Consent

Participants will provide written consent using procedures approved by the Institutional Review Board (IRB) of UAMS. Recruitment will be done over the phone by the Central RA/care coordinator. Patients who are interested in participating will be asked to meet in person with a Site RA for about 1 hour. When the patient arrives for their appointment, the Site RA will review the consent form, answer any questions, obtain written consent, then administer the brief baseline in-person interview. Informed consent documents will be composed at a fifth grade or lower reading level, be summarized, followed by a brief "teach back" to confirm understanding of key points of consent. The formal consent of each subject, using the IRB-approved consent form, will be obtained before that subject is submitted to any study procedure.

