The Principal Investigator will carefully monitor study procedures to protect the safety of research subjects, the quality of the data and the integrity of the study. Northwestern University (NU) will be used as a central location for data processing and management. Study data will be collected and managed using NU's REDCap, which is installed on secure NU servers located in HIPAA compliant data centers. UAMS personnel needing access to the data will be provided affiliate Northwestern IDs to access REDCap directly through NU's VPN. REDCap includes a user management system allowing project owners to grant and control varying levels of access to data (e.g. de-identified-only data views) for other users. Study team members will only be given access to data necessary for their project roles. For example, only those involved in scheduling and/or meeting with patients directly will have access to patient identifiers. In addition, Research Assistants (RAs) at each site (six sites total) will be assigned to their own Data Access Group which restricts access to their site's records. Each group is blinded to all other data/records. Those managing and analyzing the data will only have access to de-identified data.

Data Analysis

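### As written, arm assignment most plainly falls before written consent, from a table not said to be concealed; assignment should follow consent and baseline

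*Combined protocol and SAP*

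**What the plan says.** The Randomization paragraph (Preparation phase) states: "After the initial phone call to recruit participants, the RA will assign patients interested in participating to either the intervention" or the enhanced usual care arm. The assignment is made "based on an allocation table created prior to study recruitment", "using a simple 1:1 randomization scheme, stratified by site".

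The Recruitment section (Study Population) gives the patient's path. The Central RA/care coordinator makes the call. "If the patient is interested, the Central RA/care coordinator will ask the patient to meet with the Site RA for about 1 hour". At the clinic, "the Site RA will receive lists of interested patients and their scheduled appointment times"; the Site RA then obtains written consent and conducts the baseline interview. Randomisation appears only afterwards, and as a status already held: "Participants who are randomized to the intervention arm will also meet with the health coach for about 30 minutes".

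The Informed Consent section adds: "The formal consent of each subject, using the IRB-approved consent form, will be obtained before that subject is submitted to any study procedure".

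On access, Data Handling and Recordkeeping says "Study team members will only be given access to data necessary for their project roles" and restricts each site's RAs to their own site's records. It does not mention the allocation table. The Blinding paragraph deals with contamination and with who will recognise the arm later, not with concealing upcoming assignments.

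**The concern.** Randomisation protects the primary comparison only if entry into the analysed set after assignment does not depend on the arm. If patients are assigned after a phone call and asked for consent at a later visit, some will be lost in between. If the person seeking consent, or the patient, knows the arm by then, those losses can differ by arm.

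The plan has no means of recovering such patients. Study Design and Procedures plans follow-up only for eligible patients who have consented. The ITT definition in Data Analysis covers subjects *enrolled*, a term it does not define, so someone assigned by phone who never signs may drop out of the analysis uncounted. The planned imputation and pattern-mixture analyses cannot help, because no study data would exist for these people. ANCOVA adjusts for baseline HbA1c but not for motivation or willingness to attend, which plausibly matter in a self-management trial.

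**Working it through.** **1. Order of events.**
- Randomization paragraph: the trigger is the recruitment call, and the people assigned are patients who expressed interest.
- Recruitment section: interest is expressed on the call, and the Site RA's lists contain *interested* patients who have not yet been consented.
- The visit narrative runs greeting, explanation, written consent, baseline interview, then the coach meeting for those randomised to the intervention. No randomisation step is described.
- Joint reading: call, assignment, consent, baseline.
- Against it: the Randomization paragraph sets no latest time for assignment, and the Informed Consent section requires consent first. If assignment counts as a study procedure, the two sections conflict. If it does not, nothing prevents assignment before consent. Either way the order has to be stated.

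**2. Who assigns.** The Preparation phase introduces RAs as staff at each site or clinic. The Central RA first appears under Recruitment. In context, *the RA* therefore leans towards the clinic RA, who also takes consent and does the baseline interview. This is not stated. If it is right, the same person could know the arm while seeking consent.

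**3. Concealment.** No section says who holds the table, who can see it, or whether upcoming assignments are hidden. If the scheme is truly simple, earlier assignments say nothing about the next one, and the gap concerns sight of the table or early knowledge of the arm. If a prepared table stratified by site was forced to the stated 375 per arm, it would not be fully unpredictable. The documents do not say which applies.

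**4. Size.** The point rests on no figure in the plan. Let d be the extra share of one arm's analysed set made up of patients of a kind lost from the other arm, and g their baseline-adjusted HbA1c gap from the rest. Then bias = d × g. The documents give neither input. With *assumed* ranges:
- g = 0.5; d = 0, 5, 10, 15%: bias 0, 0.025, 0.05, 0.075 points.
- g = 1.0; same d: bias 0, 0.05, 0.10, 0.15 points.

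Against the plan's detectable difference of 0.43, the largest values are 0.075/0.43 = 17% and 0.15/0.43 = 35%. A gap of 1.0 is more than half of the stated 1.9 (if that is an SD), so the second line is an extreme case. The results only restate the assumptions.

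Check on the yardstick: with SD 1.9 and 337 per arm, 1.9 × (1.960 + 0.842) × √(2/337) = 0.41, slightly below the stated 0.43. This has no bearing on the point.

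**5. Cost of assigning on the day.** If a coach slot of about 30 minutes is held for every control patient and none is reused, 375 × 0.5 h = 187.5, or about 188 coach-hours, averaging about 31 hours for each of the six clinics (187.5/6).

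**The case against.** The best case for the plan is that assignment before consent is never stated. The consent rule is explicit, and the Recruitment section speaks of randomised participants only after consent and baseline. If the clinic RA assigns, that person first meets the patient at check-in, which weakens the sequence of call, assignment, consent. Three features also lower the risk: patients are told only that they will receive one of two models of education and support; the Site RA's list is described without any mention of arm; and the primary model adjusts for baseline HbA1c.

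Much of this stands. It means the order is inferred, not established. It does not remove the point, because the sections still need reconciling, the table is still not said to be concealed, and none of the three features prevents losses that depend on the arm.

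A reader might go further and infer that patients are randomised without consent, that staff can foresee assignments, or that the HbA1c comparison is biased with an inflated false-positive rate. The documents support none of these. They leave the order and the access unstated, and any error rate would come entirely from assumed inputs.

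One may also say that a concealed REDCap reveal is only one acceptable method. That is right; it is offered as an example.

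**Conclusion.** The point holds as an unresolved conflict between sections together with a missing safeguard, and it should be fixed. The plain, though not the only, reading puts assignment before written consent, and no section says the table is hidden from recruiting or consenting staff. Harm requires three things: assignment before consent, knowledge of the arm by staff or patients before consent is settled, and losses that differ by arm in patients whose outcomes also differ. The documents neither show nor exclude these. The size is therefore unknown, and it is zero if pre-consent losses are alike in both arms. Confidence is medium, because the order is inferred. Assigning after consent and baseline removes this route to bias whichever reading is right.

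**What to change.** Amend the Randomization paragraph so that:
- assignment is made only after written consent is signed and baseline data are saved;
- it is revealed one patient at a time from a list hidden from recruiting and consenting staff, for example through REDCap, which the trial already uses;
- the assigning role is named.

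Align the Recruitment section with that order and, with it in place, define the ITT set in Data Analysis as all patients randomised.

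The cost is a protocol amendment and a randomisation set-up, with no change to the sample size. The downside is that the arm is known only on the day, so coach time must be kept available for patients who may turn out to be controls: at most about 188 coach-hours, and less if slots are reused.

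The protocol schedules a focus group of past and present health coaches for March 2019, so enrolment may be well advanced. If it is complete, the amendment no longer helps, and ITT should not be reworded to take in people who never consented. Instead, state when assignment occurred relative to consent, report by arm the number assigned who did not consent (or say that this was not recorded), describe the primary analysis as covering consented randomised patients, and state any imbalance as a limitation. That costs a count from recruitment records.

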In Arkansas, [name] conducted a survey and queried the EHR at each of the performance sites to determine 1) the need for a standard diabetes education and self-management training curriculum such as the proposed ACP intervention, 2) modalities best suited for rural patients, including patients having land or cell phones the use of text messaging and/or patient portals to set action plans and to report back on progress. All site staff reported back current variable practices in terms of diabetes education – and all reported a high level of enthusiasm for participating in the present study. The EHR indicated 97% of patients have a cell or land line phone. Yet half of patients either did not have an unlimited texting plan, lacked familiarity with texting, or reported not wanting to receive text communications for their health. This was equally reported with regard to web-based communications. Thus, our team chose a health coach-led, telephone based approach.

Preparation phase

Research Assistants (RAs) at each site will be provided an ID and password to login directly to Northwestern University's (NU's) REDCap software. This allows for secure, straightforward electronic entry of participant responses by the RA and generation of output data files compatible with statistical programs. A staff analyst at NU will oversee the database structure and quality assurance activities under the supervision of Drs. [name] and [name]. We will register the trial protocol at ClinicalTrials.gov.

Study in-services and trainings will build on our previous experience gained in our research conducted in community clinics and will use adapted, updated, and standardized

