or they can get it at the 6 month visit, whatever is convenient for them. We considered alternative randomization schemes, including physician and clinic-level randomization, but our team carefully determined randomization at the patient level to be the most rigorous and appropriate approach. Physician level-randomization was viewed as not feasible since patients at these practices frequently see multiple providers (attendings and residents) over the course of a year, and are not 'bonded' to just one physician. Clinic-level randomization was also viewed as not an option given too few sites to assign, and the considerable diversity still seen across these practices, by size, staffing and patient population that would make it unlikely to have equivalent study arms.

Blinding. As with most behavioral interventions, it will not be possible to fully blind researchers, healthcare providers, and study subjects to intervention vs. enhanced usual care assignments. However, we have purposefully designed our trial to prevent certain threats to contamination between study arms. Patients will be told they will receive one of two models of diabetes education and self-management support. While they will not be deliberately made aware of the approach not received, we do recognize that there is an unavoidable risk of patients learning from other patients involved in the study. Similarly, physicians and other prescribers will not be intentionally made aware of their patients' study assignments. However, it is very likely that as health coaches will be trained to include monthly progress notes on patients' action plans in the EHR for providers to read, enrollment status to arm will be recognized. But neither patient nor healthcare provider will have access to any of the intervention components, as that solely resides with the health coach who will only be serving intervention patients, having no role with enhanced usual care subjects for the term of the trial. This commitment has been strongly made by UAMS and clinic leadership (see Letters of Support).

Qualitative provider/clinic barriers and facilitators to implementation

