Diabetes Distress. The Diabetes Distress Scale (DDS) is a 17-item measure of diabetesrelated emotional distress. It has four subscales corresponding to emotional burden, physicianrelated distress, regimen distress, and diabetes interpersonal distress.

Quality of Life. Patient-Reported Outcomes Measurement Information System (PROMIS) physical health (function) short form along with the PHQ-9 Depression Scale will be collected. Nurses will be notified if patients' scores indicate the need for follow-up either by the PCP or PCBHF, based on existing clinic protocol.

Clinical Outcomes

Hemoglobin A1c (HbA1c) and LDL cholesterol lab values, along with systolic and diastolic blood pressure values are collected as part of routine clinical care approximately every 3 months, and will be recorded from the medical record following each visit. *Body Mass Index.* Height and weight will also be taken from the medical record and the standard calculation for BMI applied (kg/m²). In addition, weight (in lbs.) will be recorded separately for weight gain/loss as an additional outcome.

Health Services Use

We will ask patients to self-report emergency department/urgency care visits, and hospitalizations. Dates of clinic appointments during the study period may be recorded from the medical record.

Fidelity outcomes:

Receipt of Diabetes Materials

We will ask patients whether they received all of the diabetes materials (yes/no), and if they still have them at each follow-up encounter (3 and 6 months).

Receipt of nurse/health coach counseling

We will ask patients to self-report whether their health coach/nurse reviewed the diabetes materials and/or provided counseling. Using health coach logs, we will document for each follow-

up time interval, whether the patient was reached (yes/no), and if yes, the time spent with the patient.

Provider-Patient Communication

We will ask questions adapted from the Consumer Assessment of Health Providers Survey (CAHPS)⁴¹ to evaluate the extent and quality of nurse/health coach counseling.

Perceived Helpfulness

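### The plan makes no provision for masking the person who conducts the H1-H5 interviews, which leaves avoidable interviewer bias in the secondary survey outcomes

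*Combined protocol and SAP*

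**What the plan says.** All references are to the combined protocol and SAP.

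- **Blinding.** The section states that "it will not be possible to fully blind researchers, healthcare providers, and study subjects to intervention vs. enhanced usual care assignments". The rest of it deals with contamination, what patients are told, and prescribers, who are not to be told the arm intentionally. Survey interviewers are not mentioned.
- **Randomization.** After the recruitment call, "the RA will assign patients interested in participating to either the intervention or to the enhanced usual care arm based on an allocation table". The section does not say which RA this is.
- **Recruitment.** Two roles are described. "The Central RA/care coordinator will make all pre-visit calls to eligible patients". A Site RA meets the patient at the clinic and obtains consent. "The Site RA will then collect baseline data through a structured interview". Only intervention patients then also meet the health coach.
- **Preparation phase.** RAs at each site use REDCap for "electronic entry of participant responses by the RA", and RA training covers administering the structured survey.
- **Fidelity outcomes.** At 3 and 6 months patients are asked about the diabetes materials. "We will ask patients to self-report whether their health coach/nurse reviewed the diabetes materials and/or provided counseling". Under Perceived Helpfulness they are asked about action plans at study completion.
- **Data Handling and Recordkeeping.** "REDCap includes a user management system allowing project owners to grant and control varying levels of access to data". The restriction described for site RAs is by site.
- **Data Analysis.** Surveys are collected at baseline, 3 and 6 months. The main time point for H1-H5 is 3 months. The primary outcome is HbA1c at 6 months, which Clinical Outcomes says is taken from the medical record.

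**The concern.** H1-H5 cover knowledge, self-efficacy, self-care behaviours, distress and quality of life: five of the six Aim 1 hypotheses. Their data are answers given to an RA in an interview. An interviewer who knows the arm can prompt, clarify or record answers differently without meaning to.

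The planned sensitivity analyses (as-treated data, imputation, pattern-mixture and selection models) address adherence and missing data. None addresses outcomes measured differently by arm, so the practical protection is in how the data are collected.

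The plan takes some care not to tell prescribers the arm but gives no equivalent protection to the survey outcomes. Because assignment follows the recruitment call, the arm may also exist before the baseline interview, whose scores are the covariate in the ANCOVA.

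**Working it through.** **1. Can the interviewer know the arm under the plan as written?**

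| Question | What the plan settles |
|---|---|
| Who holds the allocation table? | An RA; Central or Site is not stated |
| Who conducts the baseline interview? | The Site RA |
| Who conducts the 3- and 6-month interviews? | Not named; site RAs are trained to give the survey and enter the answers |
| Is the interviewer denied the arm? | No statement |
| Are there cues at the clinic? | Yes: coach sessions fall at about 3 and 6 months, when the surveys are also due |
| Are there cues in the questions? | Yes: materials at 3 and 6 months, and also counselling and action plans |
| Does the REDCap restriction cover the arm? | Role-based access exists; the RA restriction is by site, and an arm field is not mentioned |

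If the Site RA holds the table, the interviewer knows the arm from the start. If the Central RA holds it, nothing stops the arm from being passed on, and the clinic cues remain. Either way, unmasked interviewing is consistent with the plan.

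**2. How much could a small shift matter? (illustration only)**

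The plan gives no figure for interviewer bias and no power figure for H1-H5, so there is nothing of its own to reproduce here.

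Inputs from the plan:
- two-sided test at 5% (Data Analysis)
- 337 per arm at 6 months: 750 × 0.90 = 675, and 675 / 2 = 337.5 (Power and Sample Size Considerations)

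Assumptions:
- a differential shift of b SD in one survey outcome, with no true effect
- the 6-month n, because no 3-month n is given; 375 per arm (everyone enrolled) is the upper bound
- a normal approximation without baseline adjustment

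Formula: P(reject) = P(|Z + b·√(n/2)| > 1.96).

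At n = 337, √(337/2) = 12.98. At n = 375, √(375/2) = 13.69.

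| b (SD) | b·√(n/2), n = 337 | P(reject), n = 337 | P(reject), n = 375 |
|---|---|---|---|
| 0 | 0 | 5.0% | 5.0% |
| 0.05 | 0.65 | 9.9% | 10.5% |
| 0.10 | 1.30 | 25.5% | 27.8% |
| 0.15 | 1.95 | 49.5% | 53.8% |

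For scale, the difference detectable with 80% power is (1.960 + 0.842) × √(2/337) = 0.216 SD, or 0.205 SD at 375 per arm. A shift of 0.10 SD is thus nearly half of what the trial can detect.

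**The case against.** The strongest reply is that the plan does not show an unmasked interviewer. Assignment follows the recruitment call, and all those calls belong to the Central RA. The Site RA receives lists of names and appointment times, with no mention of arm. Allocation by the Central RA fits this text at least as well as allocation by the Site RA. A reader might infer that one person both allocates and interviews, but the documents do not say so. The gap is that they leave it open.

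Other points on this side also stand:

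- The Blinding section says only that full blinding is impossible. It does not rule out partial masking.
- A reader might infer that the fidelity questions are mixed in with the outcome scales. The item order would be in Appendix A, which is not in the text available, so this cannot be established.
- The interview is structured, RAs receive 1.5 days of training with role playing, and many items are patients' own ratings. All of this limits the room for interviewer influence.
- The SD shifts are assumed. The formula gives the same answer for a bias of that size from any source, including self-report by unblinded patients, which masking the interviewer would not remove.
- Hiding the arm in REDCap presupposes that it is stored there. The plan mentions only an allocation table.
- Masking would be neither complete nor free. Each clinic has a part-time RA who greets and escorts patients and may see who goes to the coach.

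These points limit the claim but do not close the gap. No section masks the interviewer, and training is not a substitute for masking.

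**Conclusion.** The concern holds in a limited form. The plan leaves open who allocates and who conducts the follow-up interviews, and it does nothing to keep the arm from the interviewer. Survey outcomes for five secondary hypotheses can therefore be collected unmasked by someone following the plan exactly.

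The size of any resulting bias is unknown. Its direction is probably towards the coached arm, but a reader should not infer that it must favour that arm in all five hypotheses; nothing in the documents shows this. The false-positive rates of about 10%, 25% and 49% rest on assumed shifts of 0.05, 0.10 and 0.15 SD and on the 6-month n. They show sensitivity and do not estimate what will happen.

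Nor does the point threaten the trial's main result: an interviewer cannot influence an HbA1c value taken from the medical record. This is a worthwhile improvement to the secondary outcomes.

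**What to change.** In the Randomization and Blinding sections, state that:

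1. The Central RA performs the allocation and passes the arm only to the health coach or nurse.
2. The Site RA, or whoever else interviews, has no access to the allocation table or to any arm, coach-log or tracking data, including in REDCap if stored there.
3. At baseline, 3 and 6 months, all H1-H5 scales are completed before any question on materials, counselling or action plans and, where feasible, before that visit's coach or nurse session.
4. At the end of each interview, the interviewer records whether the arm became known.

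**Cost.** This needs protocol wording, access settings, question order and a small change in site workflow, including who directs intervention patients to the coach. Both RA roles already exist, so no added staff should be needed, although the documents give no staffing costs against which to check this.

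**Limits.** Masking will be partial: patients may mention their coach, site RAs may see coach sessions, and self-report bias in unblinded patients remains. The plan should acknowledge this as a limitation of the H1-H5 results.
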